### Visit 4 (1 year +/- 1 month after Visit 2) (Approximately 45 mins): Follow Up

Medical history will be reviewed and any changes will be noted.

Eligibility and subject withdrawal criteria will be reviewed to ensure the subject still qualifies for the study.

Oral exam will occur as at Visit 1.

Radiographs (periapical radiographs) will be taken. It is within standard of care to take radiographs yearly after restoration placement.

Restorations will be evaluated by the grading investigator (an investigator other than who placed the restorations) according to Hickel criteria.

Intraoral photographs will be taken.

Visit 5 (2 years +/- 2 months after Visit 2) (Approximately 1 hour): Follow Up

A new medical history form will be completed by the subject.

Eligibility and subject withdrawal criteria will be reviewed to ensure the subject still qualifies for the study.

Oral exam will occur as at Visit 1.

Radiographs (periapical radiographs) will be taken. It is within standard of care to take radiographs yearly after restoration placement.

Restorations will be evaluated by the grading investigator (an investigator other than who placed the restorations) according to Hickel criteria.

Intraoral photographs will be taken.

#### Radiographs

All radiographs will be taken digitally following standard of care procedures, including the subject wearing a lead apron. The radiographs used in this study contain no more radiation than would be used in a customary dental procedure. It is within standard of care to take radiographs for caries screening if radiographs that are of diagnostic quality from within the past 1 year do not exist. It is within standard of care to take radiographs yearly for evaluation after restoration placement. Radiographs will be taken at the one-year and two year recalls. In the event an adverse event is suspected, it is clinically necessary, or due to a dental emergency a radiograph may be taken at the time of the AE or emergency, but it is not the norm for this trial.

At radiograph time, all female subjects will be questioned regarding pregnancy. Any responding positively at the time of screening will be excluded in accordance with the inclusion/exclusion criteria. If a subject becomes pregnant during the course of the study, radiographs will be delayed until after delivery. Subjects unwilling or unable to have dental radiographs will be excluded from the study.

Appointment	Visit 1 Screening	Visit 2 Baseline	Visit 3 6 month	Visit 4 1 year	Visit 5 2 year
Procedures					
Informed Consent Form	Х				
Demographics	Х				
Medical History	Х	Х	Х	Х	Х
Evaluate eligibility and withdrawal criteria	х	x	х	Х	х
Oral Mucosal Tissue Examination	x	x	х	Х	Х
Radiographs	If needed			Х	Х
Randomization	Х				
Intraoral Photographs		Х	Х	Х	Х
Sensitivity Assessment		Х			
Restoration Placement		Х			
Hickel Criteria Grading		Х	Х	Х	Х
Adverse Event Assessment		X	X	Х	Х
Stipend	X	X	X	Х	Х

#### Table 1. Subject Timeline

#### G) Subject Safety

1) Adverse Event Reporting

Any adverse reactions to the treatment provided as part of the study will be fully investigated and recorded, including details of the appropriate clinical action taken, and reported to both the IRB and contact person at Kerr Corporation.

#### Adverse Events

An adverse event is any untoward or unfavorable medical occurrence in a human subject, including any abnormal physical exam or laboratory finding, symptom, or disease, temporally associated with a subject's participation in the research.

Adverse events will be recorded in source documents and on case report forms. All adverse events and non-serious situations will be recorded, monitored, and reported to the IRB at time of continuing review or at the study's termination if this occurs before the study's next continuing review.

#### Serious Adverse Events

A serious adverse event is one that results in death, or is life-threatening, or results in hospitalization or prolongation of existing hospitalization, or results in a persistent or significant disability/incapacitation, or results in a

congenital anomaly/birth defect, or may jeopardize the subject's health and may require medical or surgical intervention to prevent one of the other outcomes listed above.

Serious adverse events will be recorded in source documents and on case report forms. Serious Adverse Events that meet the criteria of an unanticipated problem will be reported to the IRB within 5 business days following the Reportable New Information Policy. Serious Adverse Events not meeting the criteria for an unanticipated problem will be reported to the IRB at time of continuing review or at the study's termination if this occurs before the study's next continuing review.

#### Unanticipated Problems

An unanticipated problem is an incident, experience, or outcome that meets all of the following criteria: 1) The nature, severity, or frequency is unexpected for the subject population or research activities as described in the current IRB approved protocol, supporting documents, and the ICF(s); 2) it is related or possibly related to participation in the research; 3) it suggests the research may place the subject or others at a greater risk of harm then was previously recognized.

Unanticipated problems will be recorded in source documents and on case report forms. Unanticipated problems will be reported to the IRB within 5 business days after the PI/study team becomes aware of the problem. A Reportable New Information Form will be submitted to the IRB no later than 5 business days after the PI/study team becomes aware of the problem.

#### Unanticipated Adverse Device Effects (UADEs)

Unanticipated adverse device effect means any serious adverse effect on health or safety or any life-threatening problem or death caused by, or associated with, a device, if that effect, problem, or death was not previously identified in nature, severity, or degree of incidence in the investigational plan or application (including a supplementary plan or application), or any other unanticipated serious problem associated with a device that relates to the rights, safety, or welfare of subjects.

UADEs will be documented in source documents and on case report forms as to onset, severity, duration, management, outcome and relatedness to the test device. UADEs will be reported to the IRB within 5 business days after learning of the effect.

- H) Ethical Standards
  - 1) Institutional Review Board (IRB) approval will be obtained prior to commencing the study. The Principal Investigator will ensure that this study is conducted in full conformance with the US Federal laws and regulations, as well as the ICH's Good Clinical Practice Guidelines.
- I) Subject Participation

1) Screening

The PI or Co-Is will conduct screening examinations to identify subjects who meet the inclusion / exclusion criteria for enrollment into the study.

2) Informed Consent

[name] and/or his representative will introduce the study.

Consenting will take place in a private clinic bay area and the patient will be given as much time as he/she needs to consider participation. The participant will be invited to include or exclude any associates (e.g., loved ones) in the consent process.

Patients will be asked to read the consent form and given ample opportunity to have their questions answered. To avoid coercion, the consenting investigator will read through the copy of the consent form with the participant section by section, making sure the participant understands each section and has an opportunity to ask questions. If at any time the participant indicates s/he is not interested in participation, the meeting will end.

If after going through the consent form, the participant indicates s/he would like to discuss the study with associates or think about participating, then the meeting will be ended and the participant will be asked to contact the study when s/he makes her decision. If the participant contacts the study in the future for participation, s/he will be invited back to the clinic, and if informed consent is given at that time, study activities will begin then.

If the participant indicates s/he may be interested in participating after going through the consent form with the investigator, and the investigator determines the participant has the capacity to provide informed consent, the participant will be asked to provide informed consent at that time. Patients will certify their willingness to participate in the study by signing and dating the IRB approved informed consent document. The subject will be given a copy of the consent form.

If any new finding requires any change to the informed consent form, the subject will be re-consented.

Non-English speaking subjects will not be enrolled in the study because study staff at this time are not certified, prepared, or trained to translate or communicate in any language other than English. The study budget does not allow for the payment of translation services at this time. There are no direct benefits to this population by participating in this study.

3) Study Location

Tufts University School of Dental Medicine

Clinical Evaluation of Kerr SonicFillTM 2 vs 3M ESPE FiltekTM Supreme Ultra Universal Restorative PI: [name], DMD, MS, PhD

4) Personnel

Ongoing communication with the IRB and sponsor – The PI Obtaining consent – The PI or his representative Conducting screenings – The PI or Co-Is Placement of restorations – The PI or Co-Is Evaluation of restorations – The PI or Co-Is (who did not place restoration) Maintaining paperwork – The PI and/or study coordinator

- 5) Anticipated Study Timeline\*
  - Protocol and ICF Submission to the IRB: September 2016
  - Approval by the IRB: October 2016
  - Subject Recruitment, Screening, Enrollment and Randomization: June 2017-December 2017
  - Placement of Restorations- June 2017-January 2018
  - Initial Report- January 2018-February 2018
  - Six Months Follow up- December 2017- June 2018
  - Six Months Report- July 2018-August 2018
  - One year follow up- June 2018-December 2018
  - One year Report- January 2019- February 2019
  - Two year follow up- June 2019-December 2019
  - Final Clinical Study Report- December 2019- January 2020

\*this timeline is subject to change depending on completion of study enrollment

- 6) Payment for Participation
  - (a) Compensation

Restorations will be provided free of charge. A total stipend of up to \$245 in gift-card form will be awarded per subject in the manner as follows: \$25 at screening; \$50 at baseline; \$50 at six month recall; \$50 at one year; and \$70 at two years. Gift cards to Target will be given. The subject will not receive compensation for any missed recall appointments. Subjects will be responsible for paying all procedural costs not study related, as well as costs incurred after the study expires.

(b) Transportation

No travel reimbursement or transportation costs will be paid. Expenses, such as parking and transportation costs, will be paid by the subject at all times.

(c) Payment and Insurance Neither the subject, nor their insurance company, will be billed for any study procedures.

#### (d) Provision for Care in Case of Accident or Injury

In the unlikely event that a study patient becomes ill or is injured as a result of participating in this study and medical care is necessary, such medical care will be provided by a physician chosen by the patient. In the event of a research-related injury, compensation will be determined on a case-by-case basis by KaVo Kerr Group and Tufts University.

#### 7) Study Results

If interested, study results will be presented to a subject upon their request, either in person or via mail according to their preference, upon completion of the study. A log will be kept of the participants who are interested in receiving study results.

#### 8) Confidentiality

To ensure confidentiality of subject information, each subject enrolled in the study will be assigned a unique alphanumeric code. Subjects' files and all study paperwork will be kept in a secure, locked cabinet in a secure room when the documentation is not being reviewed. The information will only be shared between the researchers. Source documents and case report forms will be coded and free of subject names. Photographs will be taken of subject's teeth only (no facials). All HIPAA requirements will be followed. All electronic files will be kept on a password protected computer in a secure, locked office.

#### (a) Coding

Each will be assigned a subject identification number. Alphanumeric identification numbers will be assigned sequentially. The full subject identification number will consist of the three letters from the subject's initials and their enrollment number. This will be accessible by study personnel only.

#### (b) Access

Only study personnel will have access to data. Investigators will permit monitoring, audits, and regulatory inspections and will provide direct access to study related documentation.

9) Data Safety Monitoring Plan:

The study will be monitored at appropriate intervals by a trained member of the Kavo Kerr R&D clinical Research group (or qualified designee) by means of visits to the study clinic to evaluate patient charts, study data, and study photographs. Study monitoring visits will involve review of the study status and any issues related to the study. All Informed Consent forms will be reviewed for signatures and dates. Patient charts/records will be reviewed to ensure that all enrolled subjects meet the study inclusion and exclusion criteria. All CRFs will be reviewed for completeness of data entry to ensure that the study protocol is being followed, and to perform source data verification against information contained in the patient charts. Materials will be checked for adequate storage and sufficient quantity to meet the study needs.

Study personnel will monitor this trial for all safety related issues to determine whether an unreasonable risk to subjects develops. Quality control measures include routine inspection of case report forms, source documents, data tabulations, and tracking of adverse events.

#### Complaints

Complaint means any written, electronic or oral communication that alleges deficiencies related to the identity, quality, durability, reliability, safety, effectiveness, or performance of a device. Complaints will be reported in source documents and on case report forms.

10) New Findings

The subject will be informed of any significant new findings discovered during the course of this study that might influence the subject's continuation and participation in the study. Subjects will be told at a study appointment or via telephone of new findings during the study.

Cost of treatment for any new findings will not be covered by the study.

If new findings require revisions to the ICF, the subject will be reconsented.

11) Policy Regarding Replacement of Restorations

All subjects will be pre-screened by the two examiners. Participants will be advised of any dental pathology diagnosed (periapical lesions, caries, periodontal problems, etc) at that time and advised of the specific treatment(s) needed (root canal treatment, restoration, core build-up, periodontal therapy, etc). If any pathology is found, each individual must arrange to have the pathology treated at their own expense. A second examination will be scheduled to assess that treatment before these candidates are considered for inclusion in this study.

If conditions arise in which the subject requires endodontic treatment after the restoration is placed and is within the study duration (two years), the subject will be responsible for any root canal and/or post and core treatment. However, Kavo Ker Group will reimburse the School of Dental Medicine for the cost of the restoration (up to \$175 per unit depending on the type of the restoration) which will be credited to the subject towards the cost of his/her new restoration. In order to receive this level of support, study participants must attend all initial appointments and all recall appointments for the duration of the study, otherwise this policy is voided.

Before any re-treatment is initiated, a second dentist not associated with the study, will be selected by the Investigator in consultation with Kavo Kerr Group. That individual will evaluate the cause of failure and determine the need for a new restoration. The study sponsor or the School of Dental Medicine at Tufts University will not be held responsible for any retreatment when trauma or injury are determined to be the cause of failure and said failure is unrelated to participation in the study.

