#### **Biological Properties**

- Postoperative (hyper-)sensitivity and tooth vitality
- Recurrence of caries, erosion, abfraction
- Tooth integrity (enamel cracks, tooth fractures)
- Adjacent mucosa

The hypothesis to be tested is that the sonic-activated, bulk fill composite, SonicFill™ 2, will have comparable results to the traditional incremental technique composite, Filtek™ Supreme Ultra, in overall clinical acceptability and in all compared categories

II) Background and Rationale

Marginal leakage appears to be an inherent shortcoming of all dental restorations.  Various techniques have been advocated to enhance the marginal adaptation and reduce the microleakage of composite restorations. Multilayer techniques, in contrast to bulk packing methods, have decreased marginal gap formations. The size reduction of the composite material, the diminution of polymerization shrinkage, and the enlargement of the free surface area in relation to the volume are of great importance in this context.  When the whole margin area is first filled with an increment, fewer contraction gaps at the margins can be expected.

Traditional, incrementally filled dental composite material has been on the market for many years, and has been proven successful for use in posterior restorations. Traditional composite techniques require small amounts (up to 2mm) of composite be placed at a time and then light cured. This process is pain staking and time consuming. Newer products on the market are bulk fill – allowing increments of up to 5mm to be placed before light curing. Many of these products then require a capping material to be placed over them. The newer SonicFill™ 2 system is a sonic-activated, bulk fill composite that allows placement of material up to 5mm without the need for a capping layer. The sonic activated technique allows for easy placement and good adaptation of the restoration. This process also shortens the time necessary to complete a restoration, which benefits both the dental practitioner and the dental patient.

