#### Statistical analysis

Tables of descriptive statistics (counts and percentages for categorical variables, means and standard deviations for continuous variables) will be prepared to summarize the demographic characteristics of the patients, the distribution of restorations and baseline data, and to illustrate the recall and data analysis findings. Because the hypothesis of the study does not involve superiority of one technique over another, and comparable results between SonicFill™ 2 and Filtek™ Supreme Ultra are anticipated, confidence intervals will be used rather than p-values. In particular, for each evaluation category, the percentage of times that SonicFill™ 2 outperforms Filtek™ Supreme Ultra, the percentage of times that Filtek™ Supreme Ultra outperform SonicFill™ 2, and the percentage of times with equal performance will be calculated along with 95% confidence intervals. Frequency distributions will also be calculated for each combination of technique and evaluation category, along with 95% confidence intervals. SPSS (Version 22) and R (Version 3.1.2) will be used in the analysis.

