#### 2) Exclusion Criteria

Subjects will be considered ineligible for the study if they meet any criterion listed below:

- Is currently taking part in an evaluation of other dental restorative materials
- Has chronic periodontitis or rampant caries
- Teeth exhibiting clinical signs of periapical pathology
- Teeth with a history of self-reported preoperative pulpal problems
- Women who are pregnant (self-reported). It is standard of care to postpone routine dental procedures and radiographed until after pregnancy.
- Women who are breast feeding.
- Known allergy to resin composites or local anesthetics.
- An employee of the sponsor or members of their immediate family.
- Condition affecting salivary flow (e.g., salivary gland disorder, Sjögren's Syndrome)
- Any restorative treatment of the teeth involved in the study in the last 12 months.
- Are unwilling or unable to have dental radiographs or photographs taken of their dentition and soft tissues

- Any other condition which is the view of the investigator may affect the ability of a patient to complete the study.
- 3) Subject Withdrawal/Termination Criteria
  - Subjects who do not comply with the study procedures, such as returning for follow up visits may be withdrawn from the study.
  - Subjects who decide to stop participating in the study will be withdrawn.
  - Subjects who have a clinical pulp exposure during restoration visit will be withdrawn from study and standard of care procedures for pulp exposure and restoration placement will be followed and patient will be advised if they need further treatment and should be seen by a dentist outside the study (such as root canal therapy and/or crown).
  - Subjects who have external procedures or treatments performed on study teeth will be withdrawn from the study. However, if external treatment is only performed on one study tooth, the subject can still participate in the study and the remaining, unaffected study tooth will still be monitored for research purposes.
  - Unanticipated Adverse Device Effect

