#### Visit 3 (6 months +/- 1 month after Visit 2) (Approximately 30 mins): Follow- Up

Medical history will be reviewed and any changes will be noted.

Eligibility and subject withdrawal criteria will be reviewed to ensure the subject still qualifies for the study.

Oral exam will occur as at Visit 1.

Restorations will be evaluated by the grading investigator (an investigator other than who placed the restorations) according to Hickel criteria.

Intraoral photographs will be taken.

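### A study restoration that fails and is replaced outside the study drops out of the paired comparison, and no rule in the plan counts its failure

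*Combined protocol and SAP*

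**What the plan says.** **Withdrawal (protocol III.D.3).** "Subjects who have external procedures or treatments performed on study teeth will be withdrawn from the study". If only one of the two teeth was treated elsewhere, the subject may stay in and "the remaining, unaffected study tooth will still be monitored for research purposes". The rule does not separate treatment given because a restoration failed from treatment for any other reason, and it assigns no grade to the treated tooth.

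**Grading (III.F).** At Visits 2, 3, 4 and 5 the wording is the same: "Restorations will be evaluated by the grading investigator (an investigator other than who placed the restorations) according to Hickel criteria". Grading is scheduled at baseline, 6 months, 1 year and 2 years, and no unscheduled grading is provided for.

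**Analysis (III.B, Statistical analysis).** For each category the plan reports how often SonicFill 2 does better, how often Filtek does better, and "the percentage of times with equal performance will be calculated along with 95% confidence intervals". It gives no denominator and no rule for a failed, repaired or replaced restoration. The hypothesis (I.A) is that the materials are comparable "in overall clinical acceptability and in all compared categories".

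**Re-treatment (III.I.11).** "Before any re-treatment is initiated, a second dentist not associated with the study, will be selected by the Investigator". Then: "That individual will evaluate the cause of failure and determine the need for a new restoration". The section does not ask for a Hickel grade, and it does not say that the pair leaves the analysis. Credit towards a new restoration after endodontic treatment is conditional: "study participants must attend all initial appointments and all recall appointments for the duration of the study".

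**Scale (Appendix A).** Grade 5 already covers a lost or multiply fractured restoration, a fractured cusp or tooth, and a tooth needing endodontic treatment and replacement of the restoration.

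**The concern.** Each subject contributes one pair of teeth, and a better/worse/equal result needs a grade on both. When a failed restoration is replaced outside the study, section III.D.3 leaves at most one tooth under observation. This affects the analysis in two ways:

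- A restoration that fails and is replaced elsewhere between two recalls is never graded in its failed state.
- A restoration graded 4 or 5 at one recall and then replaced elsewhere counts at that recall but has no pair at later ones, including the two-year visit.

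In both cases the pair is lost because of its outcome. A failure on one side only is an unequal pair in the category that failed. Taking it out of a denominator of gradable pairs raises the equal share and lowers the other material's outperforming share, which is the direction the hypothesis predicts. What is at stake is whether the few failures, clinically the most important events in the trial, appear in the main comparison.

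**Working it through.** **The plan's own figures.** The largest 95% margin of error with n = 35 is 1.96 × √(0.25/35) = 0.1656, or 16.6%. The dropout allowance is 35/(1 − 0.20) = 43.75, rounded up to 44. Both agree with the Sample size section.

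**Gaps between gradings.** From III.F, nominally 0 to 6, 6 to 12 and 12 to 24 months, so 6, 6 and 12 months.

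**Effect of one lost failure.** Take 35 pairs in the failing category, one one-sided failure and all other pairs equal. Limits are exact (Clopper-Pearson) 95%.

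| | Failure counted | Lost, gradable pairs as denominator | Lost, all pairs as denominator |
|---|---|---|---|
| Worse | 1/35 = 2.9% (0.1% to 14.9%) | 0/34 = 0% (upper 10.3%) | 0/35 = 0% (upper 1 − 0.025^(1/35) = 10.0%) |
| Equal | 34/35 = 97.1% (lower 85.1%) | 34/34 = 100% (lower 89.7%) | 34/35 = 97.1% |

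So the rise in the equal share depends on a denominator that the plan does not state. The failure goes uncounted under either choice.

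**Several lost failures, or other unequal pairs.** With k one-sided failures and u other unequal pairs, the equal share is (35 − u − k)/35 if the failures are counted and (35 − u − k)/(35 − k) if they are lost.

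| u | k | Counted | Lost |
|---|---|---|---|
| 0 | 3 | 32/35 = 91.4% | 32/32 = 100% |
| 3 | 1 | 31/35 = 88.6% | 31/34 = 91.2% |
| 3 | 3 | 29/35 = 82.9% | 29/32 = 90.6% |
| 7 | 1 | 27/35 = 77.1% | 27/34 = 79.4% |

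With three failures all on one material and u = 0, the worse share goes from 3/35 = 8.6% (1.8% to 23.1%) to 0/32 (upper 10.9%).

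**Opposite direction.** In a category where the lost pair was equal, 28/35 = 80.0% becomes 27/34 = 79.4%.

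**Dropout allowance.** Treating more subjects does not restore the failure: 1/44 = 2.3% (upper 12.0%) becomes 0/43 (upper 8.2%).

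**How likely is at least one loss?** The documents give no failure rate and no share of failures that would be lost, so both are assumed. Let f be the two-year failure rate per restoration and s the share of failures lost, with 2 × 35 = 70 restorations treated as independent. Chance = 1 − (1 − f·s)^70.

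| f | s = 10% | s = 25% | s = 50% |
|---|---|---|---|
| 1% | 6.8% | 16.1% | 29.6% |
| 2% | 13.1% | 29.6% | 50.5% |
| 5% | 29.6% | 58.5% | 83.0% |

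These chances count every lost failure, whether or not the pair was unequal.

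**The case against.** **The event would be on record.** Adverse events are assessed from Visit 2 onward and entered on the CRF, complaints about durability or performance are recorded, and the outside dentist examines the cause before re-treatment. This stands: failures would normally be documented. But nothing in III.B, III.D.3 or III.I.11 carries those records into the paired percentages.

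**External treatment should be uncommon.** Study restorations are free, and the credit after endodontic treatment rewards attending every recall. The Risk section expects loss or fracture to be rare. This also stands. It makes the 10% column more plausible for the external route than the 50% column, for which no section gives support.

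**No decision can flip.** The plan sets no margin, test or threshold, and one lost pair moves the equal share by 2 to 3 points against a planned margin of error of up to 16.6 points. True, but when failures are few, losing one or two can remove all of them from the table.

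**Stronger readings that the documents do not support.** A reader might infer from III.I.11 that the replacement policy itself drops re-treated teeth. It does not. For in-study re-treatment the plan is silent, so the tooth could be graded as failed, graded as replaced, or left out. A reader might also infer that the loss favours comparability in every category. It does so only in the category that failed, only for a one-sided failure, and, for the equal share, only with gradable pairs as the denominator. If both teeth fail alike, the lost pair is an equal one.

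**Conclusion.** The point holds for external treatment, where the loss follows from a stated rule. III.D.3 ends paired follow-up of the tooth, grading is confined to four visits, and the analysis needs two grades. For in-study re-treatment the finding is only that the plan does not say which grade counts. A failure still in place at a recall is graded there, but its status after later replacement is undefined.

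The size is uncertain and probably small in absolute terms. It is zero if no failed restoration is replaced. With gradable pairs as the denominator, each lost one-sided failure adds about 2 to 3 points to the equal share, and a lone failure would vanish from the table (1/35 to 0/34). The chance of at least one loss runs from about 7% to 83% over the assumed inputs. It should be quoted as that range, because the documents fix neither the failure rate nor the share lost. The plan should be amended because the loss depends on outcome, tends to favour the hypothesis in the failing category, and is cheap to prevent.

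**What to change.** 1. **III.B and III.D.3.** A study restoration repaired or replaced because it failed, inside or outside the study, stays in the paired comparison for the failing category at that recall and all later ones. It takes the last blinded grade that recorded the failure or, if there is none, the Appendix A grade matching the documented event. Its other categories are missing after re-treatment, so a new restoration's luster or staining is not compared with an older one's. State the denominator for each category.
2. **Cause of failure.** For in-study re-treatment, use the second dentist's evaluation under III.I.11. That dentist cannot examine a tooth already treated elsewhere, so for external treatment use the treating dentist's records, reviewed without knowledge of the material where possible. Replacements for unrelated trauma, or for reasons other than failure, get no failure grade and are reported separately.
3. **III.I.11.** Where feasible, the existing blinded grader grades both study teeth before in-study re-treatment.
4. **Reporting.** Give by material the number of teeth re-treated and the number graded from records. Show the paired percentages with and without record-based grades.

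**Cost.** A few sentences in three sections, using the existing grader, second dentist and CRF, with no added subjects or scheduled visits. The grader must occasionally be available between recalls. Record-based grades may be unblinded, which is why item 4 asks for both analyses, and denominators will differ slightly by category.
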